8.5.5 Study Treatment Storage and Accountability

It is forbidden to use investigational drug material for purposes other than as defined in this protocol.

8.5.5.1 Study Treatment Storage

All investigational product will be stored between 2°C to 8°C ([35.6°F to 46.4°F]; see USP Controlled Room Temperature) until time of dispensing. However, storage at ambient temperature for short and/or intermittent periods of time, including transportation is accepted.

8.5.5.2 Study Treatment Accountability

All supplies of Viaskin® (active and placebo) will be accounted for in accordance with GCP. There will be an individual study drug accountability record for each subject and the Investigator will maintain accurate records of the disposition of all trial medication supplies received during the study. These records will include the amounts and dates that clinical drug supplies were received, dispensed to the subject, returned by the subject, and returned to the Investigator or destroyed on site. The unused Viaskin patches will be returned on subsequent study visits. The excessive and used study drug will be destroyed by The Children's Hospital of Philadelphia Research Pharmacy using standard protocols. The research pharmacist will provide a corresponding certificate of destruction.

8.5.6 Dose Adjustments and Dose Escalation

No dose adjustments or dose escalation are planned apart from the adjustment in the duration of application during the first weeks of treatment.

Even though the subjects should ideally reach the daily 24-hour application regimen from the 15th day of patch application onwards, for subjects who may experience some severe local reactions at the initiation of the treatment, the daily duration of patch application should be adapted/reduced if necessary, to limit the severe reactions.

In case of local unbearable skin reactions or in case of systemic allergic reactions, the Viaskin® patch should be removed immediately in order to allow the reactions to subside rapidly. The next patch would be re-applied only the following day at the expected time and the reactions will be observed. If or when the local severe reactions recur, the patch can be removed at that time. This process can be repeated the following days until the time the subject can bear the patch for 24 hours a day.

If a subject is having systemic symptoms including worsening of EoE symptoms, the subject will have return for study visit and possible decrease in daily exposure to the Viaskin patch with gradually increase in exposure as tolerated.

Only one dose is being investigated in this pilot study, at the highest dose of Viaskin Milk currently under development (500 µg of cow's milk proteins) due to the limited number of subjects to be recruited.

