8.4.3 Withdrawal and Replacement of Subjects

8.4.3.1 Criteria for Subject Withdrawal

In accordance with the Declaration of Helsinki (Appendix 1) and other applicable regulations, a subject has the right to withdraw from the study at any time for any reason without prejudice to his or her future medical care by the physician or at the institution.

Subjects may withdraw from the study/schedule of assessments for any of the following reasons:

- Adverse Event. The patch treatment will be temporary discontinued for any subject with Grade 4 local skin reactions possibly, probably, or definitely related to the investigational product.
- A subject will be discontinued from further participation in the study for >2 grade 4 local skin reaction possibly, probably or definitely related to investigational product

- The Investigator decides that it is the subject's best interest to be withdrawn from the study.
- The subject is unwilling to continue in the study (consent withdrawal).
- Lack of compliance with protocol requirements and procedures.
- The Sponsor- Investigator or Regulatory Authorities, for any reason, stops the study.
- The subject fails to return to the clinic for scheduled visits and does not respond to telephone or written attempts at contact (lost to follow-up).
- Subject's death

The reason for withdrawal will be recorded in the clinical records and the electronic Case Report Form (eCRF) and reported annually in the IND Annual Report (21 CFR 312.33). All subjects who are withdrawn or discontinue should be provided with alternative medical care, if applicable.

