8.4.3.2 Study Stopping Rules

Study enrollment will be suspended pending an expedited safety review by an independent DSMB if any of the following occur:

1. Any death related to Viaskin® dosing.
2. Any Stage 3 anaphylaxis related to Viaskin® application.
3. Marked increase in EoE symptoms with daily vomiting or severe abdominal pain in more than one patient
4. ≥ 1 SAE related to the investigational product or a study intervention
5. ≥ 2 Grade 3 AEs related to the investigational product

Upon safety review, one of the following outcomes will be determined:

- Accrual to the study may continue without modification.
- Accrual to the study may continue with modifications as prescribed by the DSMB.
- Accrual to the study should be discontinued.

All actions will be reported in compliance with local and federal regulations.

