8.5 Treatment

8.5.1 Treatments Administered

The Investigator must ensure that the investigational product will be used only in accordance with the protocol.

Following the confirmation of milk-induced Eosinophilic Esophagitis at screening, subjects will be randomized in a 3:1 ratio at Visit 4 (Day 1) into two different double-blind treatment groups to receive EPIT with Viaskin® Milk (500 µg of milk proteins) or placebo.

Repeated daily application will be made from Day 1 up to Month 9 at which time milk will be re-introduced into the diet of the subjects. The treatment will then continue during the milk re-introduction period (for 1 week to 2 months) up to the last endoscopy and biopsy. In total, the subjects can therefore receive the study treatment for up to 11 months.

Application of the Viaskin® patch will be made with progressive increase duration of application at the start of treatment: 6 hours/day during the first week, 12 hours/day during the second week, and for an entire 24 hours daily from the third week (Day 15) onwards. During the period of 24 hours of daily application, flexibility of 24 hours ± 4 hours of daily application is permitted.

For all subjects (4-17 years), the patch will be applied on each side of the spine in the inter-scapular area. The specific place where one Viaskin® is administered will represent a “Zone”. In total, six zones will be used in each subject to apply the Viaskin® : the first Viaskin® will be applied on zone 1, the second Viaskin® on zone 2 (after removal of Viaskin® 1), etc. until all six zones have been used, and the dosing will continue with zone 1, zone 2 etc.

O 1	O 4
O 2	O 5
O 3	O 6

Once applied to the skin, Tegaderm® must be used to cover the Viaskin® to prevent it from coming off. Other dressings could also be used as an alternative to Tegaderm® as allowed by the Principal Investigator.

In case the Viaskin® comes off, or after removing a Viaskin®, it is recommended that the subjects or subject's parent(s) thoroughly wipe off the zone with a moist disposable napkin or a disposable tissue and wash their hands to prevent accidental transmission of allergenic protein. If possible, the subject could take advantage of their shower time to change the Viaskin®. The previous Viaskin® is removed before the shower (or bath) and discarded, and the new one applied a few minutes after the shower (or bath) and after careful drying the skin.

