8.5.7 Prior and Concomitant Therapy

All medications used in the last 6 months or being administered at the time of screening and along the study will be recorded on the appropriate eCRF pages.

Application of a topical corticosteroid to treat any local AE (eczematous lesions, pruritus, edema, etc.) is allowed. An ointment with 1% hydrocortisone will be distributed to each randomized subject at discharge on Day 1 (V4). In case the 1% hydrocortisone ointment is not sufficient to treat the local reaction, an ointment containing a more potent corticosteroid can be prescribed and locally applied. Should skin reactions not be resolved by topical steroid, see Section 8.5.6 above.

Oral antihistamine or oral corticosteroids are allowed to treat AE determined as being allergic reactions. These treatments should be limited in time and stopped as soon as the AE has resolved. The Investigator will determine the best choice of treatment(s), the dose and the regimen according to the subject's age, and the type and the degree of severity of the reaction. Cetirizine is recommended as the oral antihistamine of choice. Medications will be documented in the concomitant medication log (including dosage, duration, and indication.). It is expected the subjects will maintain constant medications for asthma and allergic rhinitis during the trial.

All other treatments prescribed by the Investigator or any other physician to treat an AE are also permitted. Administration of concomitant medications must be reported in the appropriate section of the eCRF along with dosage information, dates of administration, and reasons for use. Generic names for concomitant medication should be used. The total daily dose should be provided.

Prohibited Treatments during participation in the study include:

- Any investigational drug or device other than Viaskin Milk or placebo
- Swallowed corticosteroids or anti-leukotrienes
- Beta-blocking agents, angiotensin-converting enzyme inhibitors, angiotensin-receptor blockers, calcium channel blockers or tricyclic antidepressant therapy
- Immunotherapy to any food or aeroallergens
- Anti-TNF or anti-IgE drugs (such as omalizumab), or any other biologic immunomodulatory therapy

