12.11 Adverse Events of Special Interest

AEs of special interest in this study include Grade 4 local skin reactions upon application and removal of the Viaskin®. Skin reactions at the site of Viaskin® Patch application will be examined at the time points specified at each visit and graded according to Section 11.13 (Table 5). Specifically, the appearance of any vesicle(s) or ulcerative skin lesion(s) or any other significant skin lesion which could potentially lead to skin barrier disruption at sites of Viaskin® applications will be considered AEs of special interest. Any occurrence of systemic (or distant) allergic reaction related to Viaskin® Milk application will also be considered an AE of special interest.

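### Section 8.5.6 has the patch re-applied the day after a systemic allergic reaction without putting the return visit first, and the zone rotation makes no exception for broken skin

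*Protocol*

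**What the plan says.** **After a reaction (Protocol 8.5.6).** The third paragraph covers unbearable local skin reactions and systemic allergic reactions together. The patch comes off at once, and "The next patch would be re-applied only the following day at the expected time and the reactions will be observed". The sentences that follow, about repeating this daily until the child can wear the patch for a full day, speak of local reactions. The fourth paragraph deals with systemic symptoms, including worsening EoE: "the subject will have return for study visit and possible decrease in daily exposure to the Viaskin patch", followed by a gradual increase. It sets no deadline for that visit.

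**Grade 4 reactions (8.4.3.1).** "The patch treatment will be temporary discontinued for any subject with Grade 4 local skin reactions" where these are possibly, probably or definitely related. More than two such reactions end participation. The length of the pause and the condition for restarting are not given. For reactions that outlast topical treatment, 8.5.7 says: "Should skin reactions not be resolved by topical steroid, see Section 8.5.6 above". Section 8.5.6 does not mention Grade 4.

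**Zones (8.5.1).** Patches move through six sites in order "until all six zones have been used, and the dosing will continue with zone 1, zone 2 etc".

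**Skin integrity.** Section 12.11 makes an adverse event of special interest of "the appearance of any vesicle(s) or ulcerative skin lesion(s) or any other significant skin lesion which could potentially lead to skin barrier disruption". Section 6.4.2 reports that, in animals, epicutaneous treatment on stripped skin increased the Th2 response and eosinophil infiltration, whereas treatment on intact skin reduced them. Exclusion 15 bars children with generalized skin disease and no intact zone.

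**Study level (8.4.3.2).** "Study enrollment will be suspended pending an expedited safety review by an independent DSMB if any of the following occur"; the list includes "Any Stage 3 anaphylaxis related to Viaskin® application".

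**The concern.** Most patches are applied at home, by families with children as young as 4. Later double-blind visits are three months apart (Months 3, 6 and 9), with calls in between. In that setting the written instruction decides what happens the next morning. For a systemic allergic reaction, the timed instruction is to put on the next patch; the visit has no time attached. A family that follows the text exactly can re-expose the child before anyone has judged whether that is safe.

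The rotation raises a similar problem. The protocol treats intact skin as important in its preclinical rationale, in an exclusion criterion and in its list of special-interest events, but no dosing rule carries this forward. A patch can fall due on a zone that still has vesicles. In the protocol's own animal data, compromised skin pushed the response towards the disease under study.

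**Working it through.** No design figure is involved. The check sets the sections side by side and works out the timing they imply.

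**1. Which 8.5.6 paragraph applies to a systemic reaction?** Section 10.1 says a systemic reaction in this trial would appear as worsening EoE, with abdominal pain and possible vomiting. The fourth paragraph names worsening EoE as a systemic symptom. Both paragraphs can therefore apply to the same child, and only re-application carries a time.

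**2. How long is the window?** If the next patch goes on at the usual hour the following day:

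time to next patch = 24 h − hours already worn

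| Worn before removal | Left before next patch |
|---|---|
| 3 h | 21 h |
| 6 h | 18 h |
| 12 h | 12 h |
| 20 h | 4 h |

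The return visit comes first only if it falls inside the right-hand column.

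**3. Does the stopping rule hold the patch?** No. It suspends enrollment, and its three possible outcomes all concern accrual. None addresses the affected child's next dose.

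**4. When does a zone come round again?** With six zones, one patch a day and a pause of p days:

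interval = 6 + p days

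For p = 0, 1, 3, 7 the interval is 6, 7, 9, 13 days. The documents give no healing time, so this is an assumption shown as a range. If healing takes 6, 7, 10 or 14 days, the smallest pause with 6 + p at least that long is 0, 1, 4 or 8 days. Rotation alone is enough if skin heals within 6 days. Beyond that, avoiding an unhealed zone depends on a pause whose length is not stated.

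**5. What do pauses cost in compliance?** Section 8.5.8 has two standards: more than 80% sought over the treatment period, and non-compliance defined as under 80% in any visit-to-visit interval.

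*Whole period*, nine months taken as about 274 days:
- 7 missed: 267/274 = 97.4%
- 14 missed: 260/274 = 94.9%
- 54 missed: 220/274 = 80.3%; 55 missed: 219/274 = 79.9%

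*Visit to visit*, using nominal visit days:
- Visits 4 to 5, about 7 patches: 2 missed, 5/7 = 71%
- Visits 5 to 6, about 22 days: 5 missed, 17/22 = 77%; 7 missed, 15/22 = 68%
- Visits 6 to 7, about 61 days: 14 missed, 47/61 = 77%

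A pause that barely registers over nine months can make a child non-compliant in an early interval. Section 8.5.6 anticipates severe local reactions at the start of treatment, when these intervals are shortest. Protocol 13.5.3 and SAP 4.1 give compliance below 80% as an example of a major deviation without saying which standard applies.

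**The case against.** The best defence is that the two paragraphs of 8.5.6 should be read together. The repeat-dosing sentences concern local reactions, and a visit that may lower exposure makes sense only if it precedes re-exposure. The following-day wording can also be read as a minimum delay. This is a fair account of what was probably intended, but the text leaves the order open and families act on instructions derived from it.

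Other safeguards exist: three hours of observation after the first patch and one hour at Visit 5; wear time stepped up from 6 to 12 to 24 hours in both periods; stopping rules that also cover marked EoE worsening in more than one patient, related serious events and related Grade 3 events; and the investigator's freedom to reduce wear or withdraw a child. Active IgE-mediated milk allergy is excluded, and 10.1 reports no systemic reactions with the Viaskin patch. These points make events unlikely, but none sets a restart rule for the individual child. The Investigator's Brochure, the safety management plan and the family instructions were not available and may contain such rules; 8.5.6 does not refer to them for re-dosing.

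The timing arithmetic only restates the schedule, and the healing times are assumed. It shows how the gap could arise, not how often it would.

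A reader might infer from the cross-reference in 8.5.7 that a related Grade 4 reaction is also re-patched the next day. The documents do not support that: 8.4.3.1 requires a pause and governs. The missing restart criterion is closer to missing detail, since investigators would be expected to end a pause sensibly.

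**Conclusion.** The point holds as an inexpensive patient-safety improvement that should be made. Followed to the letter at home, 8.5.6 can re-expose a child after a systemic allergic reaction before assessment, with as little as 4 hours to arrange a visit if the patch had been worn for 20. The rotation in 8.5.1 can bring a patch back to a zone with vesicles or open skin after 6 days plus any pause. The Grade 4 restart condition is a smaller, related gap.

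Two further inferences should be resisted. One is that the trial's results are at risk: nothing here bears on the primary endpoint, and no distortion of the per protocol set is shown. The other is that added pauses cost nothing in compliance because 7 or 14 missed days still leave 97% or 95%. That is true only over the whole period; the visit-to-visit definition in 8.5.8 can be breached by 2 missed patches in the first week. Only persistent non-compliance may lead to withdrawal, so this affects how the remedy is written and does not weaken the safety case.

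The conclusion assumes that no unsupplied document already sets the order. Without a Grade 4 or systemic reaction rate for this population, the number of children affected cannot be estimated. Systemic events are expected to be rare.

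**What to change.** Three short additions:

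1. **Protocol 8.5.6.** *After a systemic allergic reaction, including a worsening of EoE symptoms that the investigator, once contacted, judges possibly related to the patch, no further patch is applied until the return visit has taken place and the investigator has cleared re-application, at reduced daily duration if needed. Next-day re-application applies to local reactions below Grade 4 only; related Grade 4 reactions follow 8.4.3.1.*
2. **Protocol 8.5.1 and 8.4.3.1.** *Any zone with vesicles or open skin is skipped until healed. After a related Grade 4 reaction, patches restart once the investigator confirms that the zones to be used are intact.*
3. **Protocol 8.5.8 and the per protocol definition in Protocol 13.5.3 and SAP 4.1.** *Pauses ordered by the investigator for a reaction do not count as non-compliance.*

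The investigator's judgement in the first clause keeps ordinary abdominal pain from stopping treatment automatically. The third clause prevents a safety pause from counting against the child.

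The cost is a few protocol sentences, one SAP clause, a revised instruction to families, one unscheduled check per event and some missed patch days. No scheduled visit is added; the return visit for systemic symptoms is already required and is simply held before the next patch.

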8.5.7 Prior and Concomitant Therapy

All medications used in the last 6 months or being administered at the time of screening and along the study will be recorded on the appropriate eCRF pages.

Application of a topical corticosteroid to treat any local AE (eczematous lesions, pruritus, edema, etc.) is allowed. An ointment with 1% hydrocortisone will be distributed to each randomized subject at discharge on Day 1 (V4). In case the 1% hydrocortisone ointment is not sufficient to treat the local reaction, an ointment containing a more potent corticosteroid can be prescribed and locally applied. Should skin reactions not be resolved by topical steroid, see Section 8.5.6 above.

Oral antihistamine or oral corticosteroids are allowed to treat AE determined as being allergic reactions. These treatments should be limited in time and stopped as soon as the AE has resolved. The Investigator will determine the best choice of treatment(s), the dose and the regimen according to the subject's age, and the type and the degree of severity of the reaction. Cetirizine is recommended as the oral antihistamine of choice. Medications will be documented in the concomitant medication log (including dosage, duration, and indication.). It is expected the subjects will maintain constant medications for asthma and allergic rhinitis during the trial.

All other treatments prescribed by the Investigator or any other physician to treat an AE are also permitted. Administration of concomitant medications must be reported in the appropriate section of the eCRF along with dosage information, dates of administration, and reasons for use. Generic names for concomitant medication should be used. The total daily dose should be provided.

Prohibited Treatments during participation in the study include:

- Any investigational drug or device other than Viaskin Milk or placebo
- Swallowed corticosteroids or anti-leukotrienes
- Beta-blocking agents, angiotensin-converting enzyme inhibitors, angiotensin-receptor blockers, calcium channel blockers or tricyclic antidepressant therapy
- Immunotherapy to any food or aeroallergens
- Anti-TNF or anti-IgE drugs (such as omalizumab), or any other biologic immunomodulatory therapy

8.5.8 Treatment Compliance

It is the Investigators' responsibility to ensure that subjects are correctly instructed on how to take their study medication. Records of study medication used and intervals between visits will be kept during the study. Subjects will be asked to return their unused medication (box(es)) when they come back for their study visits. All unused medication (boxes) should be returned at the end of the study. The study drug will be dispensed by the Investigator, or by a qualified individual under the Investigator's supervision. An up-to-date treatment inventory/dispensing record must be maintained (see Section 8.5.5.2).

At each visit, prior to dispensing trial medication, previously dispensed trial medication will be retrieved by the Investigator and compliance assessed. A compliance of > 80% over the treatment period is sought. Subjects exhibiting poor compliance as assessed by counts and response to the question "Did you take your Viaskin® regularly?" will be counseled on the importance of good compliance to the study dosing regimen.

Non-compliance is defined as taking less than 80% of trial medication during any evaluation period (visit to visit). Subjects who are persistently non-compliant may be withdrawn from the study.

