8.4.3.3 Evaluations at Withdrawal

For any subject who is withdrawn before completing all study visits, the Investigator should:

- Perform an end of study visit: all subjects who are withdrawn early from the trial will undergo the procedures planned for Visit 17 (see Section 9). End of study visits will be performed no later than 2 weeks after withdrawal/discontinuation.
- Complete all appropriate subject Diary and eCRF pages, providing the date and explanation for the subject's withdrawal/discontinuation.
- When indicated, arrange for appropriate follow-up and/or alternative medical care of the discontinued subject.

If the subject fails to attend for a scheduled end of study visit, there will be at least two attempts to contact the subject via telephone and written communication. If these receive no reply, the subject will be considered lost to follow-up.

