13.2 Sample Size Estimation

This is a pilot study in which we aim to identify efficacy of the Viaskin® Milk treatment. Sample size is based on projected subject volume. If efficacy is shown, our pilot data could be used to perform a power analysis for a larger study.

We will recruit 38 subjects and plan to have approximately 22 evaluable subjects with milk-induced EoE confirmed by endoscopy and biopsy.

A total sample size of 22 evaluable subjects (16 subjects in the active Viaskin® Milk group and 6 subjects in the placebo group) will achieve 90% power to detect a difference of 40 in mean maximum eosinophil counts between the two treatment groups (mean maximum eosinophil counts of 10 and 50 in Viaskin® Milk and in placebo, respectively) assuming that a common standard deviation is 20 using a two group *t*-test with a two-sided significance level of 0.05.

Approximately 22 subjects will be randomized to obtain 18 completed subjects with 10% drop-out.

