### **3.3 Missing data**

Every attempt must be made by the Investigator to provide complete data. The primary analysis can be performed on data without imputation. However, exploratory analyses using various imputation techniques (i.e., last observation carried forward (LOCF)) will be utilized to assess the robustness of the data. Analyses of secondary efficacy measures will be based on the intent-to-treat (ITT) population with missing values imputed using the last value carried forward analysis.

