#### 4.1 Analysis populations

The analysis populations are:

- **Safety population:** The safety population is comprised of all subjects who are randomized and received at least one dose of study treatment and all subjects in the control group who did not withdraw or were not withdrawn. This population will be used to assess comparative safety information.
- **Intent-to-treat population:** The intent-to-treat (ITT) population (full analysis set) is comprised of all subjects who are randomized. Subjects in the ITT population will be categorized by their randomized treatment assignment. This population will be used to assess comparative efficacy information.
- **Per protocol population:** The per protocol (PP) population includes all subjects in the ITT population who do not have pre-defined major deviations from the protocol that may affect the primary (and secondary) endpoints (i.e., subjects who have not gone through the third upper endoscopy and biopsy at the end of the double-blind treatment, subjects with a compliance below 80%, etc.). The PP population will be used to perform confirmatory analyses of the primary efficacy evaluation.

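### Children withdrawn for poor patch use or skin reactions have no Visit 10 biopsy, and conflicting missing-data rules leave the ITT primary analysis open to bias of unknown size and direction

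*Protocol*

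**What the plan says.** - **Poor patch use.** Protocol 8.5.8 sets the line at 80% of patches between visits and provides for counselling. It then states: "Subjects who are persistently non-compliant may be withdrawn from the study". Section 8.4.3.1 lists "Lack of compliance with protocol requirements and procedures" among the withdrawal reasons.
- **Skin reactions.** Under 8.4.3.1 a related Grade 4 reaction leads to a temporary stop of the patch. Beyond that: "A subject will be discontinued from further participation in the study for >2 grade 4 local skin reaction". The first rule (8.5.8) is discretionary; this one is worded as mandatory. Both concern leaving the study, not only stopping the patch.
- **What a withdrawn child undergoes.** Section 8.4.3.3: "all subjects who are withdrawn early from the trial will undergo the procedures planned for Visit 17", within two weeks. The Visit 17 list in 9.13 contains no endoscopy or biopsy. Section 8.4.3.4 rules out replacement. Nothing in the protocol asks for a Visit 10 biopsy once patches have stopped.
- **Analysis sets.** Protocol 13.5.2 and SAP 4.1 put every randomized child in the ITT set, and the SAP adds: "Subjects in the ITT population will be categorized by their randomized treatment assignment". Both documents treat a missing third endoscopy, and compliance under 80%, as per-protocol exclusions. Such children therefore remain in ITT by name.
- **Missing data.** SAP 3.3: "The primary analysis can be performed on data without imputation". It keeps last observation carried forward (LOCF) for exploratory checks and for the secondary measures. Protocol 13.6.1 opens with the same permission but then applies LOCF to primary and secondary measures alike. The SAP's Table 7 specification, for the primary ANCOVA, mentions LOCF without making clear whether it covers one population or both.

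**The concern.** An ITT set of all randomized children protects the comparison only if their outcomes are sought. Here two rules tied to patch use and patch tolerance can end follow-up before the only biopsy that supplies the primary endpoint. These children are counted in ITT but contribute no observed outcome.

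What happens next depends on which missing-data rule is followed. Without imputation, the ANCOVA drops them and the comparison is between biopsied children. With LOCF, a screening biopsy stands in for a post-treatment one, because no study biopsy is scheduled between screening and Visit 10. In the usual visit order the last screening biopsy is the milk-free one, which must be 0 to 10 eosinophils/HPF for eligibility. That is a value from a different diet, and it looks like treatment success.

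With about six placebo children, a few selective losses could shift the primary result.

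**Working it through.** **Inputs.** Protocol 13.2: active mean 10, placebo mean 50, SD 20, 16 active and 6 placebo, 22 randomized to give 18 completers. It claims the sample "will achieve 90% power to detect a difference of 40 in mean maximum eosinophil counts between the two treatment groups", "using a two group *t*-test with a two-sided significance level of 0.05". SAP 3.2: 15 + 5 randomized, 18 completers. Eligibility criterion 4: milk-free biopsy of 0 to 10.

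**Step 1. The plan's own power.** Noncentrality = 40 / (20 × √(1/n₁ + 1/n₂)), exact noncentral t.

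- 18 completers at about 3:1 (14 + 4, my split): 2/√(1/14 + 1/4) = 3.53 on 16 df, power 91.1%. The stated 90% reproduces.
- 16 + 6: 2/√(1/16 + 1/6) = 4.18 on 20 df, power 97.8%.
- 15 + 5: 95.5%.

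So 90% matches the completers, not the numbers printed beside it. Planned loss is 4/22 = 18.2% in the protocol (which calls it 10%) and 2/20 = 10% in the SAP. That is a separate matter to reconcile.

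**Step 2. No imputation.** Assume k of 16 active children are removed and would have had mean M, the rest average 10, and no placebo child is lost. The all-randomized active mean is [(16 − k) × 10 + k × M]/16, and the true difference is 50 minus that. The biopsied children show 40 throughout.

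| k | M = 10 | M = 30 | M = 50 | Overstatement at M = 50 |
|---|---|---|---|---|
| 1 | 40 | 38.75 | 37.5 | 2.5 (40/37.5 = 1.07) |
| 2 | 40 | 37.5 | 35 | 5 (40/35 = 1.14) |
| 4 | 40 | 35 | 30 | 10 (40/30 = 1.33) |

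At M = 50, simulated power with all 22 biopsied is 94%, 88% and 69% for k = 1, 2, 4. Without the removed children it is 97%, 97% and 96%.

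**Step 3. Direction when there is no effect.** Both means 50, SD 20, 16 + 6, removal from active only, 100,000 simulated trials. The nominal rate of a false result in favour of active is 2.5%.

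| Who is removed (2 or 4 active) | Shift towards active, eos/HPF | False result favouring active |
|---|---|---|
| At random | 0 or 0 | 2.5% or 2.6% |
| Removal correlated 0.5 with the count | 2.2 or 4.0 | 4.5% or 6.4% |
| Highest counts (worst case) | 4.4 or 8.0 | 8.9% or 17.8% |
| Lowest counts | −4.3 or −8.0 | 1.5% or 0.8% |

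**Step 4. LOCF with the milk-free biopsy.** Same no-effect setting, with removal at random and a carried value averaging 5.

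- 2 active removed: active mean (14 × 50 + 2 × 5)/16 = 44.4, a shift of 5.6 towards active. The simulated false-result rate is 4.5%.
- 4 active removed: (12 × 50 + 4 × 5)/16 = 38.75, a shift of 11.25. The rate is 9.4%.
- If one placebo child is also removed, the placebo mean is (5 × 50 + 5)/6 = 42.5. The shift becomes 42.5 − 44.4 = −1.9 (against active) with 2 active removed, or 42.5 − 38.75 = +3.75 with 4.

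LOCF can therefore create bias even when removal is unrelated to outcome. Its direction depends on how losses split between arms, and on which screening biopsy came last, since Protocol 8.1 lets the clinical physicians set the order.

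**The case against.** A reader might infer that the ITT primary analysis is simply a completers analysis that favours active. The documents do not support that.

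- **Completers.** This is true under SAP 3.3 only. Protocol 13.6.1 also prescribes LOCF for the primary analysis, and even the no-imputation sentence is a permission.
- **Which arm.** The compliance rule covers both arms under blinding. Only the Grade 4 rule plausibly falls more on active. The support is the earlier milk-patch pilot of a related product (Protocol 6.4.2), where localized eczema was more frequent on active. Yet topical steroid was used in one patient per group, and no child interrupted treatment for an adverse event.
- **Outcome link.** No text says that reactions or poor use go with higher counts. Protocol 13.5.3 accepts that low compliance may affect the endpoint but gives no direction. Section 8.5.6 allows reduced exposure when EoE symptoms worsen, so low exposure and poor outcome could coincide. That is suggestive only.
- **Frequency.** Non-compliance withdrawal is discretionary, for persistent cases, with counselling. Reactions are first met by shorter wear, re-application, topical treatment and a temporary stop. The per-protocol exclusion for compliance under 80% implies that many such children are expected to stay.
- **Size.** The four planned losses cover every cause and both arms. Putting all four on active at a count of 50 is an extreme case.

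These points defeat any claim about direction or a firm size. They do not supply the missing biopsy, and LOCF does not repair the gap.

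**Conclusion.** The concern holds in limited form. The protocol permits study withdrawal for persistent poor patch use and requires it after more than two related Grade 4 reactions, with no primary biopsy at exit. Depending on which written rule is followed, the ITT primary analysis then either contains only biopsied children or substitutes a screening count.

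The size and direction of the bias are unknown. It could favour active if skin reactions fall mainly on active and the removed children would have had higher counts. The overstatement of 2.5, 5 or 10 eosinophils/HPF rests on 1, 2 or 4 removals, all on active, all with a mean of 50. It is zero if removed children resemble those who stay, and the bias reverses if low-count children leave. How many children these rules would remove cannot be derived from the documents.

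**What to change.** 1. In Protocol 8.4.3.1 and 8.5.8, delete lack of compliance with patch use as a reason for study withdrawal, and handle it through the per-protocol set, which already lists it. Keep these children on the planned schedule through Visit 10 unless consent is withdrawn or the investigator judges further procedures unsafe. Include their data in the ITT analysis and record the patch stop date.
2. Leave the Grade 4 patch-stopping rule as it is. The sponsor should reconcile its wording about leaving the study with the ITT definition, so that outcome data are sought only where consent and the investigator's safety judgment allow.
3. Reconcile Protocol 13.6.1, SAP 3.3 and the Table 7 specification into one primary missing-data rule that does not carry a screening biopsy forward.

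**Cost.** Protocol, SAP and consent wording. The ITT effect may be smaller. Some children with poor or stopped patch use would still have the planned milk reintroduction and research endoscopy under sedation or anesthesia, which withdrawal would have spared them. The consent form and the IRB must cover that.
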